# 4.3 Withdrawal of Subjects

Subjects who do not become pregnant at the end of the intervention or usual care component (21 months postpartum) are still included in the study. They will not undergo further evaluation but will continue to be followed until either they become pregnant or the study terminates. Contact will be maintained through a brief monthly check-in phone call from study staff. For the intervention arm, this will include a reminder of body weight goal and strategies to sustain weight loss. Testing will resume during pregnancy at the specified intervals of 12-16 and 32 to 36 weeks of pregnancy.

• Describe anticipated circumstances under which subjects will be withdrawn from the research without their consent.

We have had subjects we asked to withdraw from the study because of their not returning for their metabolic assessments in the metabolic research centers, no shows at scheduled training sessions, smoking (which is an exclusion criteria).

If a LIPP subject becomes pregnant prior to 16 weeks after randomization or becomes pregnant before the 3-month postpartum randomization, i.e. no baseline measurement, they would be asked to withdraw.

• Describe procedures that will be followed when subjects withdraw or are withdrawn from the research, including the possibility of partial withdrawal from study intervention with continued data collection.

We will plan to maintain demographic data for subjects who have withdrawn from the study in order to compare with subjects who have been compliant with the study protocol in order to determine if there was bias in subject compliance.

• Include any necessary safety precautions to be applied to subjects who withdraw or are withdrawn (tapering drug doses, evaluative x-ray, etc.). NA

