canopy system. Participants will relax in a quiet low-light metabolic room for 30 min prior to obtaining a 30-min measure of exhaled breath. Oxidative glucose metabolism will be estimated and urine samples will be obtained before and after the measure in order to calculate non-protein RQ (NPRQ). These data will be used in conjunction with Specific Aim 2 and will be correlated with placental mitochondrial function during pregnancy.

Exercise Capacity: An incremental graded treadmill test will be performed at baseline (3), 6, 9, 15, & 21 months postpartum time points in both groups. In addition, for the intervention group additional VO2 max testing will be performed at approximately 4 & 5 months postpartum. Oxygen consumption, heart rate, and ratings of perceived exertion will be performed as previously described (48, 64, 65, 72).

Insulin Sensitivity and  $\beta$ -Cell Function: A 75 g oral glucose tolerance test (OGTT) will be used to assess postprandial glycemia, and insulin sensitivity and secretion. After an overnight fast, blood samples will be drawn at -10, 0, 30, 60, 90, 120, & 180 minute time points. C-peptide data will be analyzed using a combined model approach to provide prehepatic insulin secretion rates, insulin sensitivity, disposition index, and relate insulin and C-peptide kinetics (73). Plasma glucose will be measured using the glucose oxidase method (YSI; Yellow Springs, OH). Insulin will be assayed by RIA (Millipore, Billerica, MA). A fasting blood sample will be collected in lieu of the OGTT during pregnancy visits when there is a lack of funding. The OGTT will be collected during pregnancy again if additional funding is secured.

Enteroinsular Axis Responses: Plasma samples (with appropriate additives) will be obtained to measure incretin hormones (glucagon-like peptide-1 (GLP-1), and glucose-dependent insulinotropic polypeptide (GIP), and satiety-related gut peptides (cholecystokinin (CCK), and peptide YY (PYY). Measurements will be made under static (fasting) and dynamic (glucose-stimulated) conditions. Blood samples for these incretin measurements will not be collected when there is a lack of funding, but may be collected again if additional funding is secured.

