exercising and to notify the investigators if there is any change in their medications (prescription, over-the-counter, herbals) during the period of this study. All exercise sessions will be recorded in an exercise training log and supervised by a certified exercise physiologist/trainer. There are cases where this supervision may occur remotely if necessary.

- Dietary Intervention (Weight Maintenance): During the first phase of weight maintenance (2A) subjects will attend approximately 2 supervised group sessions per week. Each session will last approximately 60 minutes. These sessions will include structured exercise (e.g., Zumba, jazzercise, stroller walking) and we will review subjects' diet records.
- After 3 months and the desired weight loss, subjects will move to the next Phase (2B). During this phase, subjects will be required to attend approximately 1 supervised session per week. If they do not maintain their weight loss, they will return to the previous phase for more supervised weight management. Alternatively, if they maintain their weight loss after 3 months, they will progress to the third Phase (2C) of the program until they become pregnant.
- The third phase (2C) consists of no supervised exercise sessions. However, subjects and their Lifestyle Coach will talk on the phone weekly to review their progress, including FitBit exercise data, weight, and diet. Each telephone call is expected to last approximately 5 minutes.
- Electronic Diet Data Collection: Dietary assessment is a standard-of-practice for clinical trials. The ASA24, or Automated Self-Administered 24-hour (ASA24) Dietary Assessment Tool, is a web-based tool that enables multiple, automatically coded, self-administered 24-hour dietary recalls. The ASA24 guides participants through steps to record all foods and beverages they have consumed over 24-72 hours. The ASA24 was developed by the National Cancer Institute at the National Institutes of Health and has been validated for accuracy.
- Participants will be assigned an ASA24 ID, Username and Password from each study site.
- The 24-hour recall usually takes 20–30 minutes, a similar length of time if an in-person 24-hour recall was conducted.
- The format and design of the ASA24 are modeled on the interviewer-administered Automated Multiple Pass Method 24-hour recall developed by the US Department of Agriculture (USDA). This recall requires multi-level food probes to accurately assess food types and amounts.

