#### **5.2** Procedures

• Is there a placebo control arm?

🗹 Yes 🛛 🗆 No

If Yes, describe the following:

- *The scientific, methodological, and medical reasons to use a placebo.* There is no placebo per se. We are using the term usual care.
- The care that will be given to subjects who receive placebo. If this is local standard of care, specify that.

Local standard of care plus more detailed information about healthy eating and exercise from study staff at the time of the visits or via electronic communication.

- o All potential risks to the placebo group and how the risks will be minimized. NA
- Provide a description of all research procedures being performed as follows:
  - How individuals will be screened for eligibility. Specify screening that will take place prior to informed consent and screening that will take place after informed consent.
     Screening before consent will be performed by a review of the delivery logs on Labor and Delivery on a daily basis using the screening log form. Contact information with be obtained and the subjects who express interest before their postpartum visit will be met by study staff to review in detail the study objectives, protocol and procedures.
  - Procedures being performed to monitor subjects for safety or to minimize risks.
     Study subjects in the intervention arm will have frequent contact with lifestyle trainers and nutritionists initially approximately 3 times/week, then approximately 2 times, then approximately one time per week in person. Assuming the subject is maintaining her weight contact will then be continued with frequent phone calls and via email, text or downloading of data from Fit Bit.
  - All drugs and devices used in the research, their regulatory approval status, and the purpose of their use. NA
  - The source records that will be used to collect data about subjects. (Attach all surveys, scripts, and data collection forms.)

Please see attached documents.

- Describe the following concerning pregnancy testing and birth control:
  - Whether pregnancy testing will be conducted on women of reproductive potential? If testing will not be conducted, provide the reason.
     Pregnancy testing will be determined on all pregnant women at the time of metabolic visits.
     Additionally, a POC test will be performed by LIPP staff when a VO2max test is done outside of the metabolic visit. We will not do pregnancy testing once the subjects enter the pregnancy component of the study.

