# 6.6 Provisions to Monitor the Study to Ensure the Safety of Subjects

- Describe the plan to periodically evaluate the data regarding both harms and benefits to assess subject safety as follows: We will continue to have a DSMB to evaluate subject benefit and harm.
  - Study data, including safety data, untoward events, and efficacy data, will be reviewed on a regular basis.

Please refer to the DSMB charter.

- Who will review the data? The DSMB this will include representatives from Case Western Reserve in Cleveland, TMC in Boston and PBRC in Baton Rouge. This has been made available to the IRB
- How the safety information will be obtained and documented (e.g., case report forms, by telephone calls with participants, printouts of laboratory results, etc.).
   Per the format laid out in the DSMB which was in place in Cleveland.
- The frequency of data collection, including when safety data collection starts.
- Safety collection starts when the first subject is enrolled into the study, in particular for the intervention group starting training.
- The frequency or periodicity of review of cumulative data. This will depend on how there is progression of recruitment. In Cleveland we had a DSMB approximately twice in the first year of the grant. We will have a minimal of 1 DSMB meeting per year.
- The statistical tests for analyzing the safety data to determine whether harm is occurring. The LIPP study statistician who will be located at Pennington Biomedical in Baton Rouge will determine this.
- Any conditions that trigger an immediate suspension of the research or other action for the research.

Any severe adverse reaction will trigger a review and determination if this was related to the research protocol.

- The plan might include establishing a data monitoring committee which addresses all the above.
- Describe the entity responsible for monitoring the data, and their respective roles (e.g., the investigators, the research sponsor, a coordinating or statistical center, an independent medical monitor, a Data and Safety Monitoring Board (DSMB) /Data Monitoring Committee (DMC), and/or some other entity, and the timeframe for reporting events to this entity.
  - Submit a copy of the DSMB/DMC Charter if the study is monitored by a DSMB/DMC. We have submitted the DSMB Charter for the LIPP study in Cleveland as well as the two DSMB reports (both open and closed) to the Tufts Medical Center IRB.

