The risks to subjects are minimal. They are the standard of care we should provide to all our obese patients considering future pregnancy. Our ability to provide more than a minimal amount of information is hampered by the lack of resources particularly for women seeking care without considerable personal resources. If successful, as proof of principle, we believe this protocol can serve as a paradigm for a wider initiation of lifestyle interventions before pregnancy.

- *How any risk of this research is the least possible for achieving the objectives of the research?* Risk will be minimized by having trained lifestyle intervention staff supervise physical activity and nutritionist the healthy eating for the Intervention group. The usual care group will receive benefit from having specific goals provided by our research team but not specific follow-up per the study protocol.
- How mothers providing consent are informed of the reasonably foreseeable impact of the research on the fetus or neonate.

Mothers are informed by the PI of the study and potential benefits of healthy eating and exercise before pregnancy. They will also be informed of the foreseeable impact of the research on their fetus/neonate.

- Specify that no inducements, monetary or otherwise, will be offered to terminate a pregnancy and that in the case of a fetus, the fetus is not the subject of a planned abortion. NA
- Specify that individuals engaged in the research will have no part in any decisions as to the timing, method, or procedures used to terminate a pregnancy or in determining the viability of a neonate. NA

Will the research involve neonates of uncertain viability or non-viable neonates?

🗆 Yes 🛛 🗹 No

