### PROTOCOL TITLE: Lifestyle Intervention in Preparation for Pregnancy (LIPP) VERSION DATE: March 31st, 2023

- Symptoms and risk related to normal pregnancy progression such as nausea, vomiting, fatigue, urinary frequency, increased or decreased appetite, transient dizziness, mild back or breast pain or discomfort, mild mood changes, miscarriage, preterm delivery, still birth, low birth weight, problems with placenta and birth defects,
- Symptoms related to fasting for at least 8-hours and related hypoglycemia: headache, nausea, and lightheadedness
- Symptoms related to hypoglycemia such as fainting, fast heart rate, sweating, shakiness, difficulty paying attention, sudden moodiness or irritability, unconscious
- Symptoms related to venous blood draw such as bruising, bleeding, swelling, and pain, fainting, lightheadedness and infection at the injection site.
- Symptoms related to consuming the glucose solution for the diabetes testing such as brief nausea, vomiting, tiredness, lightheadedness and upset stomach.

\* While the above medical events may be expected, they will be collected for outcome purposes.

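### From 3 to 21 months postpartum the safety-monitoring text schedules between-visit contact for the LIPP arm alone and writes no common adverse-event query, so maternal events are expected to be recorded more often under LIPP.

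*Combined protocol and SAP*

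**What the plan says.** Section 5.2, under the prompt on procedures to monitor subjects for safety, says: "Study subjects in the intervention arm will have frequent contact with lifestyle trainers and nutritionists initially approximately 3 times/week". Contact then falls to about two and about one in-person contact a week, and later to phone, email, text or FitBit downloads. Usual-care women do not appear in that answer.

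Section 5.1 (LIPP group) gives the detail: supervised exercise on 3 to 5 days a week for 12 weeks, about two sessions a week in phase 2A and about one in phase 2B. In phase 2C, which runs until pregnancy, "subjects and their Lifestyle Coach will talk on the phone weekly to review their progress". LIPP women are also told to inform the trainer if they think they may be pregnant.

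Both arms share metabolic visits at 3 (baseline), 6, 9, 15 and 21 months postpartum. The usual-care text in 5.1 says that study staff will monitor these women, but gives no interval and no content. For women not pregnant at 21 months, in either arm, section 4.3 says: "Contact will be maintained through a brief monthly check-in phone call from study staff".

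Section 7.1 covers all adverse events in both arms. Its list of expected events includes miscarriage, with the note "While the above medical events may be expected, they will be collected for outcome purposes". Section 6.6 starts safety collection at first enrolment, "in particular for the intervention group starting training", and leaves the choice of safety tests to the study statistician. Sections 6.6 and 7.2 refer to the DSMB charter for procedures.

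**The concern.** An adverse event reaches the database only if someone learns of it. A LIPP woman speaks to study staff at least weekly until she conceives. On the written schedule, a usual-care woman may go six months without a contact. A sprain, a dizzy spell, a short illness or an early loss is therefore likely to be heard of promptly in one arm. In the other it is heard of only if the woman remembers it or volunteers it at the next visit. Staff are not blinded (section 8.5 blinds only the statistician), so unstructured questioning offers no protection.

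The cost runs both ways. An apparent excess of maternal events or miscarriage in the arm that is losing weight before conception could come from ascertainment alone and mislead the DSMB. Equally, a real excess caused by the exercise programme could be put down to closer observation. As written, the data could not separate the two.

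**Working it through.** **1. Visit schedule.** Section 4.4.3 states a maximum of seven visits, five postpartum and two in pregnancy. The schedule reproduces this: 3, 6, 9, 15 and 21 months, plus 12-16 and 32-36 weeks, gives 5 + 2 = 7. Four postpartum visits follow baseline, with gaps of 3, 3, 6 and 6 months (18 in total). A six-month gap is about 26 weeks, or about 32 if the ±3-week windows fall at opposite ends (26 + 3 + 3).

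**2. LIPP contacts over those 18 months (about 78 weeks).** The inputs are the phase rates in 5.1. I assume on-time progression (12 weeks, then two 3-month phases of about 13 weeks) and no pregnancy. The remainder is 78 − 12 − 13 − 13 = 40 weeks.

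- Low: 12×3 + 13×2 + 13×1 + 40×1 = 115
- High: 12×5 + 13×2 + 13×1 + 40×1 = 139

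From month 6 to month 21 alone this is 26 + 13 + 40 = 79 LIPP contacts, against the three visits in that period that both arms have. A woman who conceives earlier has fewer; one sent back to an earlier phase has more.

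**3. What else could equalise ascertainment in months 3 to 21.**

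| Provision | Covers both arms? | Is it a safety query at a common interval? |
|---|---|---|
| Usual-care monitoring by staff (5.1) | Controls | No interval or content |
| Questionnaires at visits (5.1) | Yes | General health, pain and limitations; not adverse events; same sparse visits |
| All adverse events documented (7.1) | Yes | States scope, not how events are elicited |
| Monthly call (4.3) | Yes | Starts only after 21 months |
| Fortnightly breastfeeding texts (11.2.1) | Opt-in, both arms | Feeding only |
| Record access (6.5) | Yes | Limited to screening and the outcome pregnancy and delivery |

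None of these supplies a common adverse-event query between 3 and 21 months.

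**4. Illustrative size.** Suppose that true event rates are equal and constant, and that the chance of an event being reported decays with half-life *h* weeks until the next contact. The share reported over a gap of *g* weeks is (1 − e^(−λg))/(λg), with λ = ln 2/*h*. LIPP uses *g* = 1. Controls use the four gaps, weighted by length. The half-life is my assumption; the documents give none.

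| *h* (weeks) | LIPP share | Control share | Ratio |
|---|---|---|---|
| 4 | 0.918 | 0.278 | 3.3 |
| 8 | 0.958 | 0.464 | 2.1 |
| 13 | 0.974 | 0.600 | 1.6 |
| 26 | 0.987 | 0.762 | 1.3 |
| 52 | 0.993 | 0.869 | 1.1 |

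The direction is the same throughout; only the size changes. The model treats every LIPP contact as an opportunity to report, which is generous for a five-minute coaching call. It describes events before pregnancy. For early losses I claim direction only: a LIPP pregnancy is likely to be known to staff soon after the woman suspects it, whereas pregnancy visits in both arms start only at 12-16 weeks, after viability is confirmed.

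**The case against.** The strongest reply is that closer supervision of the exercising arm is part of the intervention, that all adverse events are to be documented regardless of arm, and that the operating detail sits in the DSMB charter and attached forms, which may already contain a common query. The point about the charter stands: if it holds such a query, a cross-reference is enough. The general commitment in 7.1 does not answer the concern, because it does not say how an event in a usual-care woman comes to be known between visits.

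Some stronger readings are tempting, and the documents do not support them.

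- **That only LIPP women are monitored.** The usual-care text, section 7.1 and the monthly call in 4.3 all say otherwise. What is missing is a schedule and a common query.
- **That the LIPP-only sessions, where VO2 "max testing will be performed at approximately 4 & 5 months postpartum" with a pregnancy test, inflate recorded losses.** They fall inside the contraception period (at least 7 months post-delivery in 5.2; to the 6-month visit in 2.2). They also precede the withdrawal limit of 16 weeks after randomisation, about 6.7 months postpartum, and 4.3 mentions keeping only demographic data after withdrawal. They would mainly reveal withdrawals.
- **That sparse pregnancy testing is a control-arm problem.** From month 6 the scheduled tests are the same in both arms, and LIPP exercise sessions require none.
- **That 6.6 commits the trial to a between-arm test.** The words "The statistical tests for analyzing the safety data to determine whether harm is occurring" are the form's prompt; the study's reply only names who will decide.
- **That 6.10 denies controls safety follow-up.** The phrase "but not specific follow-up per the study protocol" concerns lifestyle goals.

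It is also fair that setting aside events found at LIPP sessions could hide real exercise harm. The fix has to guard against that.

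**Conclusion.** The concern holds as a matter of unequal ascertainment between 3 and 21 months postpartum. Scheduled contact between the shared visits is about 115 to 139 sessions or calls under LIPP, and none is scheduled under usual care. No common query is written in the protocol. With equal true rates, maternal adverse events, and early losses before the first pregnancy visit, are expected to be recorded more often under LIPP.

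The size cannot be fixed from the documents. The illustrative ratio of 1.1 to 3.3 rests wholly on the assumed half-life, and the contact count assumes on-time phases and no pregnancy within 18 months. The conclusion would fall away if the charter already requires the same query in both arms. SGA and preterm delivery, the safety endpoints named in 8.1, are delivery outcomes and are not affected.

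**What to change.** In sections 5.2 and 6.6:

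1. Ask the same scripted adverse-event and pregnancy/pregnancy-loss questions in both arms at every shared visit, including the two pregnancy visits. If the DSMB charter already requires this, cite the charter section instead.
2. Record the source of each event. Make the main between-arm safety comparison on events from the common query, plus the outcome-pregnancy and delivery records that 6.5 allows staff to access. Show all events by arm and source to the DSMB and in the final report, including those learned only at LIPP sessions, coach calls or LIPP-only VO2max visits, so that true exercise harm stays visible.

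The cost is one short form and a source flag in REDCap. The main comparison leaves out some LIPP events, which are reported separately. Because the trial is under way, events collected before the change should be flagged as such. The common query still relies on recall over gaps of up to six months, but it does so equally in both arms. Starting the monthly call of 4.3 earlier in both arms would shorten that recall; it is optional and the fix does not depend on it.

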# 2.2 Risks to Subjects

#### Adequacy of Protection Against Risks

Risks include the following:

Subjects will be asked to use an acceptable means of birth control at least until they have completed the 6month post-partum follow-up visit. The type of birth control they choose will be determined by them and their health care provider. There are no risks in performing the metabolic studies when pregnant; they will be performed at 12-16 and 32-36 weeks of pregnancy. We would not wish to perform them outside the defined study windows to avoid extra visits or obtaining blood that cannot be used as part of the research.

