#### 4.4 Recruitment and Retention

# 4.4.1 Local Recruitment Methods

Describe the following attributes of the recruitment plan for the local Tufts site:

- When, where, and how potential subjects will be recruited.
- We plan to approach subjects, assuming they and their newborn are stable, on the postpartum unit of Tufts Medical Center (Tufts MC) after their delivery. The PI and/or

the study coordinator will inform the subjects about the study. Subjects will be identified as being eligible based on information obtained at the time of their delivery. Potential subjects will be interviewed by the PI and/or the study coordinator to determine eligibility and potential interest in the LIPP project. They will be given a brochure describing the study. If potentially interested we will obtain contact information, such as email and phone numbers and contact potential subjects prior to their 4-6 week postpartum visit. Before their postpartum visit with their OB health care provider, study staff will contact them to determine if they might be interested in participating in the LIPP study. If they are, one of the recruiters will meet the subject at their postpartum visit, explain the study in more detail, and provide the potential subject with a copy of the consent form. The subjects will have until 3 calendar months (+/- 3 full weeks) to decide to join the study and be scheduled for metabolic testing. We created an IRB-approved informational website that is linked to on the MIRI lab page at Tufts MC and distributes ads via social media and print linking to the informational website. If a potential participant would like to ask questions related to the study to a current or former participant, LIPP study staff will initiate this communication (via email, text or phone call) with the approval of both individuals.

- *Source of subjects (for example, patient population, local community, etc.).* Postpartum patients at TMC.
- *Methods that will be used to identify potential subjects.* Review of EMR charts. Patients who are found to meet exclusion criteria during screening, such as history of HIV, or hepatitis B or C, will not be recruited and their PHI will not be recorded.
- *Materials that will be used to recruit subjects.* Primarily brochures and speaking with potential subjects, as well as sharing the study website page with those who are interested. The brochure will be given to all potential subjects until we have reached our recruitment goals.

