# 5 Study Design

# 5.1 Study Timelines

- Describe the duration of an individual subject's participation in the study.
  - The time that the subject will be in the study is variable. The minimum time is 13 months (4 months in study and 9 months of pregnancy). The maximum time is 28+ months. The pre-pregnancy component of the study is variable. We list 18 months in study/21 months post-partum but if the subject becomes pregnant after 21 months post-partum, she will be followed in the pregnancy component. Hence, we list 28+ months.
- Describe the duration anticipated to enroll all study subjects at the Tufts study site. Subjects will have their initial testing and randomization 3 calendar months (+/- 3 full weeks) after their delivery. Enrollment begins when the Informed Consent is signed.
- Describe the estimated date for investigators to complete this study (complete primary analyses). The initial grant ended on 11/30/2022 and we are on an approved no-cost extension until 11/30/2023.
- Describe the study procedures that will be accomplished at each study visit. At the HNRCA, CTRC or BWH Research Facility, the following metabolic testing/procedures will be performed:

Metabolic evaluations will be performed at baseline (3 months  $\pm$  3 full weeks postpartum). Follow-up evaluations will be performed after 6 ( $\pm$  3 full weeks) and 9 months ( $\pm$  3 full weeks), 15 ( $\pm$  3 full weeks) and 21 months ( $\pm$  3 full weeks) prior to pregnancy (Figure at the top of the protocol form) up to a maximum of 18 months. Once a subject becomes pregnant and has dating and viability confirmed by ultrasound, metabolic evaluations will continue at 12-16 and 32-36 weeks of gestation. However, if an individual participant has scheduling issues or there are extenuating circumstances with scheduling visits, we may schedule outside of the above windows.

Maternal Body Composition: Anthropometry measurements will include height, weight, and hip and waist circumferences. Total body fat will be measured by whole body plethysmography (Bod Pod; Cosmed, Rome, Italy), (70). We will use a hydration constant of 76% for fat free mass during late pregnancy (71). If a BodPod is not available we will use skin calipers to take skinfold measurements of the triceps and mid-axillary skinfold to estimate body fat.

Resting Energy Expenditure: Resting Metabolic Rate (RMR) will be determined after an overnight fast using the Cosmed OMNIA metabolic cart (Cosmed, Rome Italy) with a

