  - What birth control methods women of reproductive potential will be instructed to use. If women will not be instructed about acceptable methods of birth control, clarify why.
     Subjects are instructed to use birth control for at least 7 months post-delivery. The choice of birth control will be noted but the choice will be up to the subject and her medical provider.
  - What birth control methods **men** of reproductive potential will be instructed to use. If men will not be instructed about acceptable methods of birth control, clarify why. NA
- Specify which procedures, tests, visits, etc. described above are part of usual standard of care at Tufts and which are performed solely for research purposes. All the studies obtained as part of the protocol are for research purposes.

Subjects will be given a copy of their results to share with their health care provider.

• Clarify which tests are routinely performed for clinical care, but are providing data for the research, and which tests are only performed for research purposes.

None of the testing performed as part of the protocol is for clinical purposes. Subjects are free to share the information, for example, the results of the OGTT, with their health care provider.

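### The two stated contraception minimums differ, and neither is tied to the 16-weeks-after-randomisation withdrawal limit; the 7-month floor ends about 11 days short when randomisation is 3 weeks late

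*Combined protocol and SAP*

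**What the plan says.** Three provisions bear on this, and they run on different clocks.

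- **Contraception, Section 5.2 (Procedures).** The clock starts at delivery: "Subjects are instructed to use birth control for at least 7 months post-delivery".
- **Contraception, Section 2.2 (Risks to Subjects).** The end point is a visit. Women will be asked to use "birth control at least until they have completed the 6month post-partum follow-up visit".
- **Withdrawal, Section 4.3.** The clock starts at randomisation: "If a LIPP subject becomes pregnant prior to 16 weeks after randomization", she would be asked to withdraw.

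The timing of randomisation is not fixed. Section 5.1 says "Subjects will have their initial testing and randomization 3 calendar months (+/- 3 full weeks) after their delivery", and Section 4.4.1 gives women "3 calendar months (+/- 3 full weeks) to decide to join the study". For the later visits, Section 5.1 says "Follow-up evaluations will be performed after 6" months, again with a window of 3 weeks either side. It adds that where there are scheduling difficulties "we may schedule outside of the above windows".

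The eligibility list in Section 4.1 requires contraception to be in use by randomisation but does not say for how long. No section reconciles the two minimums or lengthens either of them after late randomisation.

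**The concern.** A woman can do what the protocol asks at minimum, stop contraception, conceive, and then be asked to leave the trial after she has been randomised. These women join because they plan another pregnancy (Section 4.1), so some may stop close to the minimum.

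The stake is retention in the neonatal fat mass comparison, which Section 8.2 describes as intent-to-treat. On women who leave, Section 4.3 says "We will plan to maintain demographic data for subjects who have withdrawn from the study". It does not say whether neonatal measurements continue. A withdrawal of this kind could therefore cost an outcome, and clearer wording of the contraception instruction would avoid it.

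**Working it through.** The plan gives no derivation of the 7 months, so there is no stated calculation to reproduce. The figure does agree with randomisation at 3 months plus the minimum of 4 months in study given in Section 5.1 (3 + 4 = 7).

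**Inputs**

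- Month: 30.44 days on average (a convention used here).
- Randomisation: 3 months after delivery, up to 21 days late within the window (Sections 4.4.1 and 5.1). 3 × 30.44 = day 91.3.
- Withdrawal limit: 16 weeks = 112 days after randomisation (Section 4.3).
- Section 5.2 floor: 7 × 30.44 = day 213.1.
- Section 2.2 floor: the 6-month visit, nominally 6 × 30.44 = day 182.6.

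**Formula**

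Gap = (91.3 + days late + 112) − contraception floor. A positive gap means that the floor ends before the withdrawal limit.

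**Section 5.2 floor**

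| Randomisation | Limit (day) | Floor (day) | Gap (days) |
|---|---|---|---|
| On time | 91.3 + 112 = 203.3 | 213.1 | −9.8 (covered) |
| 21 days late | 203.3 + 21 = 224.3 | 213.1 | +11.2 |

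The gap opens once randomisation is more than 213.1 − 203.3 = 9.8 days late. With real calendar months across all delivery dates, the on-time margin is 8 to 11 days and the gap at 21 days late is 10 to 13 days. The background text in Section 2.1 gives a window of 27 days rather than 3 weeks. At 27 days late the gap would be 230.3 − 213.1 = 17.2 days. The 3-week window in the operational sections is used for the main figure.

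**Section 2.2 floor, if used alone, randomisation on time**

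- 6-month visit on time: 203.3 − 182.6 = 20.7 days (20 to 23 by calendar).
- 6-month visit at the late end of its window, day 203.6: 203.3 − 203.6 = −0.3, no gap.
- 6-month visit at the early end, day 161.6: 203.3 − 161.6 = 41.7 days.

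The latest in-window 6-month visit (day 203.6) still comes before day 213.1. The Section 2.2 floor is therefore shorter than 7 months for every visit held in its window.

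**The case against.** The best defence is that both instructions are floors. A woman who uses contraception for 7 months satisfies Section 2.2 as well, and Section 5.2 is the direct answer to the protocol form's question on birth control, whereas Section 2.2 is a sentence in a discussion of risk. A reader might infer that the two sections contradict each other. They do not in that sense: they state different minimums that can be met together. The 21-day figure applies only to a woman who is told the Section 2.2 minimum and not the other, and nothing shows that this happens.

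Second, 7 months suits the nominal design and leaves a margin for on-time randomisation. The Section 5.2 gap needs three things together: randomisation more than about 10 days late, stopping at the floor, and conception within at most about 11 days. All of this stands, and it limits the size of the point. It does not remove it, because a date fixed from delivery cannot follow a randomisation date that may move by 3 weeks.

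Third, Section 8.2 already allows for 50% dropout. That allowance concerns numbers and is no reason to keep an avoidable cause of withdrawal. Equally, a reader might infer that the gap biases the comparison between arms or costs power. The documents give no conception rate for these days and nothing to suggest that the arms would differ, so neither inference is supported.

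Finally, a reader might date pregnancy from the last menstrual period, which would widen the gap. No section applies that dating to the withdrawal rule, and becoming pregnant ordinarily means conception.

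**Conclusion.** The point holds in a narrow form, and it is minor. Two sections state different contraception minimums, and neither is tied to the withdrawal limit. The 7-month minimum is sufficient for on-time randomisation and falls about 11 days short at the late end of the 3-week window. The 6-month-visit minimum, taken alone, falls about 21 days short at nominal timing.

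These figures assume average month lengths, pregnancy dated from conception, and a woman who stops exactly at the minimum. The number of women affected cannot be computed from the documents. The consent pages were not available for this review, so what women are actually told may be clearer than the protocol text. A reader might also infer that neonatal data are certainly lost for these women. Section 4.3 names demographic data as kept and does not say whether neonatal measurements continue, so that loss is possible but not established.

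**What to change.** Put one rule in Sections 2.2 and 5.2: contraception until the later of 7 months post-delivery or 16 weeks after the woman's own randomisation date. Change the consent wording to match if it differs. A woman who follows this rule would not meet the withdrawal limit, apart from contraceptive failure. Because the rule follows her own date, it also covers randomisation outside the window.

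The cost is one sentence in each section.

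- Compared with Section 5.2, women randomised on time see no change, and those randomised late but within the 3-week window use contraception for up to 224.3 − 213.1 = about 11 more days.
- Any woman now working only to Section 2.2 would use it for about 30 more days at nominal timing (7 months against 6).

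A single fixed date would be simpler to explain but dearer. Covering every in-window case in whole months needs 8 months (8 × 30.44 = day 243.5), which adds about a month for every woman, including those for whom 7 months is enough.
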